Data will be analysed with qualitative thematic analysis following the framework approach established by Ritchie and Spencer.^{28 29} Two researchers of the project team will independently code the transcripts of five interviews. Preliminary codes will be developed both inductively and deductively based on existing implementation models for PROs in healthcare.^{23–25} Afterwards, the researchers will exchange and reflect their ideas and interpretations of the transcripts. Based on these discussions, one researcher will develop a comprehensive coding framework and arrange identified categories around the major themes.³⁰ The focus is the understanding of barriers and facilitators for the use of electronic monitoring in an SPHC setting. Findings shall inform necessary requirements of patients and professional carers to develop a feasible implementation process. A multidisciplinary research team will accompany this process in several meetings to bring up alternative interpretations, give feedback and gain possibilities of reflection and to avoid bias.³¹ The final coding framework will then be applied to the whole data set. MAXQDA will be used to support data management.³²

Data from this substudy will inform phase 2 (feasibility/piloting of the intervention) of this project by helping

to identify optimal procedures for implementing a self-report ePRO into routine care. Co-designing the eIPOS intervention with staff members from SPHC services will ensure that eIPOS can help detect the needs of patients, thereby informing care processes and symptom management in routine care.

Substudy II: equivalence testing

A randomised crossover trial will be conducted to determine the equivalence of eIPOS and IPOS. Participants will complete the two versions of the IPOS in randomised order with a 30-minute waiting period between the questionnaires. The period should be long enough to not complete the second version by memory, but at the same time short enough for symptoms to not change between the two measurement points. The equivalence testing of the electronic version follows the ISPOR guidelines for testing measurement equivalence between electronic and paper-based PRO measures.³³

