collected: age, gender, nationality (German or non-German), main diagnosis according to International Classification of Diseases, 10th Revision groups (cancer/chronic heart disease/lung disease/others), frequency of using electronic devices, type of electronic device (personal computer, notebook, tablet, smartphone, etc), and operating system (Windows, Apple, Android, etc). Furthermore, the research team will measure the time (in minutes) that participants need to complete each IPOS version. After completing the electronic and the paper IPOS, the researcher will ask patients which version they prefer.

Sample size calculation

With a power of 80%, a target ICC of 0.9 and a significance level of $\alpha=0.05$, the calculated sample size is 47. Considering possible drop-outs, it is planned to include 50 participants.

Data analysis

A two-way ICC model with fixed effects will be calculated.³⁴ The Wilcoxon test will be used for comparing IPOS values of both versions and completion time. Equivalence will be established for individual IPOS items, for IPOS subscales (physical symptoms subscale, emotional concerns, communication and quality of care subscale)¹⁷ and the total IPOS score. Bland-Altman plots will be created to present the equivalence and differences between both versions visually for IPOS subscale values and the IPOS total score. To judge the amount of sampling bias, the sociodemographic details of participants will be compared with population profiles of participating sites via descriptive statistics.

Data from substudy II will inform the development of a valid and reliable eIPOS that can be implemented into routine clinical care to be tested in MRC phase 2 of this study.

Feasibility/piloting (MRC phase 2)

MRC phase 2 of this project focuses on testing procedures of the intervention (piloting), estimating recruitment/retention rates and determining the acceptability of the intervention (feasibility). Phase 2 consists of two parts (figure 1 for details of the integration within the overall study design): the intervention and implementation procedures developed in phase 1 will be tested (substudy III). Furthermore, the acceptability of the intervention will be determined using a qualitative approach (substudy IV).

Substudy III: quasi-experimental study to pilot and test the feasibility of the eIPOS intervention

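### Substudy II compares the two IPOS versions' values with a difference test that gives no size of shift, leaves single items without any planned estimate of shift, and does not use the randomised order in its written analysis

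*Protocol*

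**What the plan says.** All references are to the protocol.

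- **Aim and design** (Substudy II: equivalence testing). The aim is stated thus: "A randomised crossover trial will be conducted to determine the equivalence of eIPOS and IPOS". On the order of the versions the section says: "Participants will complete the two versions of the IPOS in randomised order". The gap of 30 minutes is justified by the competing risks of recall and of symptom change. On guidance the section adds: "The equivalence testing of the electronic version follows the ISPOR guidelines for testing measurement equivalence".
- **Role of the ICC**: the Abstract (Methods and analysis) assigns the equivalence testing to a two-way ICC model. The Sample size calculation of substudy II rests on it too: "With a power of 80%, a target ICC of 0.9" and alpha 0.05 give 47, raised to 50 for drop-out.
- **Analysis** (Substudy II, Data analysis). On agreement: "A two-way ICC model with fixed effects will be calculated". On the comparison of values: "The Wilcoxon test will be used for comparing IPOS values of both versions and completion time". On scope: "Equivalence will be established for individual IPOS items, for IPOS subscales", and the total score. On plots: "Bland-Altman plots will be created to present the equivalence and differences between both versions visually for IPOS subscale values and the IPOS total score".
- **Number of items** (Introduction): 17.

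No step in the Data analysis section uses order, period or sequence. The section does not say whether the ICC is the consistency or the absolute-agreement form.

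**The concern.** Two features of the written analysis do not fit an equivalence crossover.

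**Size of shift.** A Wilcoxon test asks whether there is any difference. A non-significant result may be imprecision, and a significant one may be a trivial shift. The equivalence question is how large the shift is and how precisely it is known. For subscales and total the Bland-Altman plots would show this. For single items nothing planned does.

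**Order.** If answers or completion times drift between the first and second questionnaire, through recall, practice or fatigue, the drift has opposite sign in the two order groups when expressed as electronic minus paper. It then spreads the paired differences, lowers the ICC and widens the limits of agreement. Two versions that are equivalent would look less so.

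Substudy II informs the eIPOS that phase 2 uses, where staff review scores and identify areas of need. A shift in a single item therefore has practical meaning.

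**Working it through.** **1. The plan's own figure.** Inputs from the protocol: target ICC 0.9, power 80%, alpha 0.05, N=47. The null ICC and the sidedness are not stated, so the stated inputs alone do not fix N. With two measurements per patient, F = MSR/MSE (between-patient over error mean square) is scaled by (1+ICC)/(1−ICC), which is 19 at 0.9 and 9 at 0.80. An exact F calculation with null 0.80 and one-sided 0.05 gives N=47 (power 0.807; at 46 it is 0.799). Two-sided it gives 59. The 47 is thus consistent with a null of 0.80, one-sided. That is an inference and is used below only for illustration. N is not disputed.

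**2. What each item-level measure shows about a shift.** Scores are standardised to total SD 1, with true ICC 0.9 and shift d in SD units (assumed).
- Consistency ICC: the version mean is removed, so it does not change. Simulation gives 0.90 at d = 0, 0.2 and 0.5.
- Absolute-agreement ICC: approximately 0.9/(1 + d²/2). At d=0.2 this is 0.9/1.02 = 0.88; at d=0.5 it is 0.9/1.125 = 0.80. Simulation gives 0.88 and 0.79.
- Wilcoxon P value: it mixes size with precision. At ICC 0.95 and a shift of only 0.1 SD it is significant in about 55% of studies of 47, although the agreement ICC is still 0.94.

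So an item shift is reflected in the ICC only if the agreement form is meant, and neither the ICC nor the P value states its size.

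**3. Effect of leaving order out.** Let g be the period effect in SD units (assumed), with the orders split about 1:1 (the ratio is not stated).
- Variance of the paired difference: 2(1−ICC) + g². At ICC 0.9 and g=0.2: 0.20 + 0.04 = 0.24, so the SD rises from 0.447 to 0.490.
- Error mean square: half of that, 0.10 + g²/2. Between-patient mean square: 2×0.9 + 0.1 = 1.9.
- Expected consistency ICC: (1.9 − MSE)/(1.9 + MSE).

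| g | MSE | ICC by formula | ICC simulated | Lower bound above 0.80, period ignored | With period term |
|---|---|---|---|---|---|
| 0 | 0.100 | 0.900 | 0.896 | about 80% | about 80% |
| 0.1 | 0.105 | 0.895 | 0.891 | about 75% | about 80% |
| 0.2 | 0.120 | 0.881 | 0.876 | about 60% | about 80% |
| 0.3 | 0.145 | 0.858 | 0.852 | about 32% | about 80% |

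Repeated simulations agree to within about 1 to 2 percentage points.

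- Bias in the mean difference: g × (imbalance in order)/n, which is zero under exact balance. With a 19/28 split and g=0.4 it is 0.4×9/47 = 0.08 SD.

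**4. Completion time.** The protocol expects 5–10 minutes per version. Assume a true difference of 1 minute and an SD of the paired difference of 2 minutes. Signed-rank power is 91% with no practice effect, 84% with a practice effect of 1 minute and 59% with 2 minutes. A rank-sum comparison of period differences between the two orders stays at 90%.

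**5. Precision available for the proposed estimate.** The 90% CI half-width is t(0.95; 46) × √[2(1−ICC)]/√47 = 1.679 × √[2(1−ICC)]/6.856. This is 0.11 SD at ICC 0.9, 0.15 at 0.8, 0.19 at 0.7 and 0.24 at 0.5.

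**The case against.** The strongest reply is that the ICC, not the Wilcoxon test, is the equivalence method, and that the two together are a reasonable pair: one for agreement, one for systematic shift. That stands. A reader might infer that the sponsor would call an item equivalent because its Wilcoxon test is non-significant. The protocol does not say so, and each item also gets an ICC.

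This also limits the harm. In simulation (n=47, assumed five-category item, true shift about 0.24 points), a non-significant Wilcoxon together with a consistency-ICC lower bound above the inferred 0.80 occurs in about 0% of studies at observed ICC 0.64–0.65, 0.5% at 0.74, 8–10% at 0.84–0.85 and 15–16% at 0.90. How often the Wilcoxon test alone misses a shift is therefore not a fair measure of the harm.

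Second, an unseen statistical analysis plan, or the ISPOR guidance to which the protocol defers, may settle the ICC form, intervals and a period term. This weakens the order point most. It weakens the first point less, because the protocol itself fixes the comparison of values and restricts the plots to subscales and total.

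Third, no passage shows that a period effect exists. Its size is assumed, and the error is conservative. This is fair. The protocol does, however, name recall and symptom change as the reasons for its choice of gap, and a practice effect on completion time is plausible.

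A reader might also infer that the unused order biases the version comparison, or that 47 is wrong. Neither follows: with balanced order the mean difference is unbiased, and 47 is reproducible under a plausible null.

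**Conclusion.** The point holds, at minor to moderate weight. The study is exploratory and has no written pass/fail rule for substudy II.

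- **Firm from the text:** values are compared with a difference test that cannot support equivalence; equivalence is promised for items while plots stop at subscales and total; order is randomised and not used. For items, the planned output is an ICC of unstated form and a P value, with no stated estimate of shift.
- **Conditional:** the loss from ignoring order depends on the assumed period effect, about 1:1 allocation, true ICC 0.9 and the inferred null of 0.80. It is small at 0.1 SD (about 80% to about 75%) and large at 0.3 SD (to about 32%). It works against showing equivalence and cannot create a false claim of it.

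**What to change.** In the Data analysis section of substudy II:

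1. Replace or supplement the Wilcoxon test on IPOS values with the period-adjusted mean paired difference, electronic minus paper, and its 90% CI, for all 17 items, the subscales and the total. Report it descriptively unless the sponsor fixes an equivalence margin in advance.
2. Include period in the ICC model and in the completion-time analysis. For time, a rank-sum test of first-minus-second differences between the two orders keeps a rank method.
3. Secondary, if no analysis plan already does so: state the ICC form (absolute agreement registers a shift) and the null ICC behind N=47, and read the lower confidence bound against that null.

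The cost is one degree of freedom for period; patients and data are the same, and at ICC 0.9 the CI half-width stays at about 0.11 SD. The drawback is that intervals for less reliable items are wide (0.19 to 0.24 SD at ICC 0.7 to 0.5), so some items may have to be reported as equivalence not shown. The agreement form is also stricter when a shift exists: the pass rate against 0.80 is 80% with no shift, 73% at 0.1 SD and 41% at 0.2 SD.

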Qualitative data will be analysed with thematic analysis following the framework approach. Quantitative analysis uses a two-way intraclass correlation coefficients model for the equivalence testing. Quantitative analysis of the quasi-experimental study will focus on the primary outcomes, recruitment rates and completeness of eIPOS. Secondary outcomes will include intraindividual change in palliative symptoms and concerns, quality of life and symptom burden.

Ethics and dissemination Approval of the ethics committee of the Ludwig Maximilian University Munich was received for all study parts. Results and experiences will be presented at congresses and in written form. Additionally, participating SPHC teams will receive summarised results.

Trial registration number NCT03879668.

Strengths and limitations of this study

- This exploratory study systematically develops and tests an electronic version of the Integrated Palliative care Outcome Scale, a valid and reliable paper-and-pencil patient-reported outcome in palliative care, for the specialist palliative home care setting.
- This protocol follows the Medical Research Council guidance on the development and evaluation of complex interventions which will increase the validity of results.
- Early involvement of stakeholders such as palliative care patients and professionals in the development phase will ensure rich data from multiple perspectives to inform a feasible intervention for this specialised setting.
- Potential sampling bias due to the convenience sample based on staff identification of eligible patients will be limited by training staff and co-designing the intervention with staff from the participating sites.

INTRODUCTION

In Germany, patients with severe and life-threatening conditions are entitled under law to receive specialised palliative home care (SPHC) since 2007.¹ Currently, over 300 SPHC teams are established in Germany, providing multiprofessional palliative care at home for patients with advanced life-limiting diseases and complex symptoms.²⁻⁴ Besides professional care focusing on symptom control, this also includes psychological and spiritual support as well as coordination between other healthcare professionals, for instance, general physicians.^{2,3}

Over the last decades, patient-reported outcome (PRO) measures have been developed for a better understanding of patient

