eIPOS, electronic Integrated Palliative care Outcome Scale; SPHC, specialised palliative home care.

Intervention group

At baseline, a study nurse will introduce the patient to eIPOS. After that, the participant will complete eIPOS every 3 days. There will be no obligation to answer each item of the eIPOS. Standardised procedures (for example: frequency of measurement, time point of introduction) will be finalised after phase 1. The information from self-reported eIPOS will be used in routine care processes of the service.

Prospective control

All patients who are cared for by one of the participating SPHC teams, but do not use the eIPOS, will serve as a control group. No additional interventions are planned for this group. However, care processes for this prospective control group might change because of staff being introduced to training around outcome measurement.

Retrospective control

A retrospective chart review will be conducted to provide information on care processes in the services before the introduction of a self-report PRO measure.

Inclusion criteria

The inclusion criteria are similar to substudy I and summarised in [table 2](#).

Recruitment

Intervention group: patients will be recruited from each participating team with the support from a study nurse. A study nurse will inform eligible patients in detail about the aims, study procedure and requirements. If the patient is interested, the study nurse will make an appointment for the introduction of the electronic system and perform the baseline assessment. The patient will need to give written consent before participation.

Outcome measures

Recruitment as well as drop-out rates, technical feasibility (completeness of each eIPOS) and the influence of eIPOS on provided care will be measured as the primary outcomes of interest.

Secondary outcomes will include change in palliative concerns, quality of life and symptom burden measured

with the eIPOS, the EORTC QLQ-C15-PAL (measuring health-related quality of life of palliative patients with cancer)³⁵ and the Edmonton Symptom Assessment Scale (assessing symptoms of palliative care patients)³⁶ at baseline and after 2 weeks.

Data extracted from medical records for both the intervention and control groups will include the number and severity of palliative symptoms and concerns and the steps taken by professionals for reducing the symptoms. Additionally, the number of unplanned hospital admissions will be collected.

Sample size calculation

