As sample size calculation in feasibility studies should not be based on the primary outcomes of interest,³⁷ the intraindividual comparison of quality of life between baseline and 2-week assessment was used as the basis for the estimation. An assumed small effect of $d=0.20$ (with a minimal clinical difference of 4–9 for the EORTC QLQ scale), power=80% and $\alpha=0.05$ for a Wilcoxon test with paired data lead to a sample size of 164. Based on an assumed drop-out rate of 30%, it is aimed to include 213 participants.

For a better understanding of the feasibility of the sample size, and the possible success of the recruitment plan, the total number of patients cared for by the participating SPHC teams (~1.275 patients/year) will be extracted as well. The control groups will include all patients cared for in the time period explained above.

Data analysis

Quantitative analysis will include descriptive analysis of the user rate of eIPOS, recruitment and drop-out rate as well as analysis of the technical feasibility based on completeness of eIPOS and number of missing values. Intraindividual changes in the secondary outcomes before and after the implementation of eIPOS will be explored using non-parametric tests (either Wilcoxon or Friedman). Number of symptoms and amount of provided care before and after the implementation of eIPOS will be compared using McNemar tests and Cochran tests for changes in proportions.

Substudy IV: acceptability of eIPOS (feasibility)

The methods and procedures will be identical with substudy I. In short, semistructured interviews with patients and focus groups with SPHC professionals will be conducted, focusing on the experience with eIPOS and the influence of it on the received/provided care.

Inclusion criteria

Participants who used the eIPOS in substudy III are eligible for the interviews. Apart from that, inclusion criteria are identical with the inclusion criteria of substudy I. Additional inclusion and exclusion criteria may be defined after analysing data of substudy I.

Recruitment

Recruiting participants for this part will be identical with the approach in substudy I.

Sample size

The same approach for the number of included participants will be followed as in substudy I.

Data analysis

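### Substudy III: 164 pairs at d = 0.20 and 80% power matches a one-sided paired Wilcoxon test, but no direction is declared; two-sided power is about 70%, or 66% at the 149 pairs left after drop-out

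*Protocol*

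**What the plan says.** The calculation is in the protocol under Substudy III, Sample size calculation. It says that "the intraindividual comparison of quality of life between baseline and 2-week assessment was used as the basis for the estimation". The inputs are d = 0.20, power 80% and α = 0.05, and they, "for a Wilcoxon test with paired data lead to a sample size of 164". The effect size carries a bracketed gloss, "with a minimal clinical difference of 4–9 for the EORTC QLQ scale". The recruitment target follows: "Based on an assumed drop-out rate of 30%, it is aimed to include 213 participants".

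The section does not say whether α is one- or two-sided, or which SD standardises d.

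No direction is given elsewhere. Under Outcome measures, "Secondary outcomes will include change in palliative concerns, quality of life and symptom burden"; the abstract has "Secondary outcomes will include intraindividual change in palliative symptoms and concerns, quality of life and symptom burden". The Substudy III data analysis section says: "Intraindividual changes in the secondary outcomes before and after the implementation of eIPOS will be explored using non-parametric tests (either Wilcoxon or Friedman").

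**The concern.** A reader who meets α = 0.05 with no further comment will normally take it as two-sided. On that reading the usual paired Wilcoxon calculation does not return 164. The surrounding text gives no cue to a one-sided test: the outcome is change, not improvement; the changes are to be explored; and one of the two candidate tests, Friedman, has no one-sided form.

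This calculation is the only basis given for the recruitment target of 213. If the test is carried out two-sided, the chance of detecting d = 0.20 is clearly below the stated 80%, and a null quality-of-life result would look more informative than it is. The drop-out allowance then lowers the number of pairs further, whichever side is meant.

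**Working it through.** **Inputs from the protocol (Substudy III, Sample size calculation):** d = 0.20, power 0.80, α = 0.05, paired Wilcoxon test, 164 pairs, drop-out 30%, 213 recruits.

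**Assumptions added here:** d = mean change / SD of change, and normally distributed changes, so that the Wilcoxon test has efficiency 3/π relative to the paired t test.

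**Method.** Effective size n_e = n × 3/π; noncentrality d√n_e; noncentral t with n_e − 1 degrees of freedom; critical value at 0.05 (one-sided) or 0.025 per tail (two-sided).

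**1. Reproducing 164.** At n = 164, n_e = 156.6 and the noncentrality is 0.20 × √156.6 = 2.50.

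| Test at α = 0.05 | Power just below | Power at required n | Required n |
|---|---|---|---|
| One-sided | 0.7994 at 163 | 0.8015 at 164 | **164** |
| Two-sided | 0.7990 at 207 | 0.8009 at 208 | **208** |

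The one-sided calculation gives the protocol's figure exactly.

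Other two-sided choices give 199 (paired t), 211 (Noether), 181 (logistic changes), 230 (minimum Wilcoxon efficiency, 0.864) and 133 (Laplace changes). None of these is 164. Other one-sided choices give 156 (paired t), 162 (normal approximation) and 166 to 167 (Noether).

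**2. Two-sided power at 164 pairs.** 0.7011. For 80% the effect would have to be d = 0.2253.

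**3. Drop-out.** 164 × 1.30 = 213.2, so the target was obtained by multiplying by 1.30. With 30% lost, 213 × 0.70 = 149.1 pairs remain. Keeping 164 pairs would need 164 / 0.70 = 234.3, that is 235 recruits.

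**4. Power at 149 pairs.** n_e = 142.3 and the noncentrality is 2.39. Power is 0.7671 one-sided and 0.6589 two-sided; 80% two-sided needs d = 0.2365.

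**5. Simulation of the signed-rank test (40,000 runs, normal changes).**

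| Pairs | d | One-sided | Two-sided |
|---|---|---|---|
| 164 | 0.20 | 0.803 | 0.703 |
| 149 | 0.20 | 0.767 | 0.659 |
| 208 | 0.20 | – | 0.800 |
| 164 | 0.225 | – | 0.797 |
| 149 | 0.2365 | – | 0.801 |

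**6. Sensitivity to the shape of the changes (two-sided, d = 0.20).**

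| Changes | 164 pairs | 149 pairs |
|---|---|---|
| Minimum efficiency 0.864 | 0.657 | 0.615 |
| Normal | 0.701 | 0.659 |
| Logistic | 0.760 | 0.720 |
| Laplace | 0.878 | 0.845 |

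**7. Sensitivity to the meaning of d.** If d uses the SD of the scores at one time point, the paired effect is d_z = 0.20/√(2(1 − r)), where r is the baseline to 2-week correlation. Two-sided, 80% power then needs 208 pairs at r = 0.50, 167 at r = 0.60, 164 at r = 0.6075 (d_z = 0.2257) and 126 at r = 0.70. At r = 0.6075, two-sided power at 149 pairs is 0.762.

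**8. Whether the 4–9 points settle it.** At d = 0.20 they imply an SD between 4/0.20 = 20 and 9/0.20 = 45. That range is too wide to show which SD was used.

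**The case against.** The strongest reply is that the stated inputs do yield 164 once α is read as one-sided, and that the protocol never says two-sided. On this view nothing stated is wrong: the sidedness is simply unstated, and it may be fixed in an analysis plan that is not shown. Neutral words such as change do not by themselves declare a two-sided test.

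A second reply is that d is undefined. With a cross-sectional d and r of about 0.61, a two-sided test at 164 pairs has its 80%; at r = 0.65 it has 84% at 164 pairs and 81% at 149. Changes with heavier tails than normal would also raise the two-sided power.

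A third is that the drop-out allowance is a separate matter and should not lend certainty to the sidedness point.

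Much of this stands. The one-sided origin is an inference, the power figures are conditional, and the drop-out shortfall is a distinct issue. What does not stand is that this is only detail left for later. The protocol publishes a complete calculation (effect, power, α, test and size), and the usual reading of it does not return the published size. The rescue through a cross-sectional d needs a correlation that the protocol does not state. And whenever 164 is the number of pairs that 80% power requires, 149 pairs fall short of it on either side.

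**Conclusion.** The concern holds. With d as mean change over SD of change and approximately normal changes, 164 pairs give 80% power only for a one-sided test at 0.05, a direction that the protocol nowhere declares. Two-sided power is about 70% at 164 pairs (66% to 88% across the distributions examined) and about 66% at the 149 pairs expected from 213 recruits (61% to 85%). If the test is one-sided, 149 pairs give about 77%.

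Confidence is medium, because the protocol does not say how d was standardised. The practical weight is minor: quality of life is a secondary outcome, explored in an uncontrolled before-after comparison, and the primary feasibility outcomes do not depend on this test.

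**What to change.** State that the quality-of-life test is two-sided and restate the calculation, for example: 164 evaluable pairs give about 70% power for d = 0.20 (mean change / SD of change), or 80% power for d of about 0.225, with a paired Wilcoxon test at two-sided α = 0.05 and approximately normal changes; the planned 213 recruits with 30% drop-out leave about 149 pairs, giving about 66% power for d = 0.20, or 80% for d of about 0.24.

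Alternatively, declare the one-sided hypothesis at α = 0.05, test quality of life that way, and report 80% power at 164 pairs and about 77% at 149.

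If d was standardised by anything other than the SD of change, give that SD and the within-patient correlation that was used.

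The cost is wording only, plus a less favourable stated power. Enrolling more patients is not needed for an exploratory outcome. If the sponsor nevertheless wanted 164 evaluable pairs, the target would be 235 instead of 213, which is 22 more; 80% two-sided power for d = 0.20 would need 208 / 0.70 = 297.1, that is 298 recruits.

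### Substudy III adds 30% to 164 instead of dividing by 0.70, so enrolling 213 leaves about 149 pairs, not the 164 needed for 80% power

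*Protocol*

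**What the plan says.** The relevant text is in the Protocol, Substudy III, Sample size calculation. The protocol chooses not to size the substudy on its primary feasibility outcomes. Instead, "the intraindividual comparison of quality of life between baseline and 2-week assessment was used as the basis for the estimation". With a standardised effect of d = 0.20, 80% power and alpha 0.05, the inputs "for a Wilcoxon test with paired data lead to a sample size of 164". The next step is the drop-out allowance: "Based on an assumed drop-out rate of 30%, it is aimed to include 213 participants". Whether alpha is one-sided or two-sided is not stated. The substudy III sections describe no replacement of drop-outs and no imputation of missing 2-week assessments.

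**The concern.** A paired test uses only patients with both assessments, so 164 is a count of complete pairs. The 30% is the share of enrolled patients expected to be lost, so the number to enrol must satisfy N × (1 − 0.30) = 164. The figure 213 looks like 164 with 30% added on top, which is a different calculation and always gives too small a number. If so, the planned enrolment does not deliver the stated 80% power under the protocol's own drop-out assumption, and the enrolment target is not the one its inputs imply.

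**Working it through.** **Inputs** (all from the Protocol, Substudy III, Sample size calculation): paired Wilcoxon test; d = 0.20; power 80%; alpha 0.05, sidedness not stated; 164 pairs required; drop-out 30%; enrolment 213.

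**Step 1: reproduce 164.** The power of the signed-rank test was taken from the noncentral t distribution. The number of pairs n is scaled by the test's asymptotic relative efficiency for normally distributed differences, 3/π = 0.955. With m = 0.955 × n, the noncentrality is 0.20 × √m on m − 1 degrees of freedom.
- One-sided alpha 0.05: the smallest n with at least 80% power is 164, an exact match.
- Two-sided alpha 0.05: the smallest n is 208.
- A paired t test would need 156 (one-sided) or 199 (two-sided).

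Of these four, only the one-sided Wilcoxon calculation gives 164. That basis is inferred from the match; the protocol does not state it.

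**Step 2: reproduce 213.**
- Adding 30%: 164 × 1.30 = 213.2, which rounds to the stated 213.
- Dividing by the retained fraction: 164 / (1 − 0.30) = 234.3, so 235.
- Difference: 235 − 213 = 22 patients. Rounding cannot account for this.

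**Step 3: what 213 yields.**
- Expected pairs at 30% drop-out: 213 × 0.70 = 149.1, which is 15 (9%) fewer than 164.
- Drop-out at which 213 still gives 164 pairs: 1 − 164/213 = 23.0%.
- If each patient independently completes with probability 0.70, the chance that 213 enrolled give at least 164 pairs is about 1.4% (binomial).
- Check on the corrected figure: 235 × 0.70 = 164.5 expected pairs.

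**Step 4: power**, with the Step 1 formula and a simulated signed-rank test (normal differences, 20,000 runs):

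| Pairs | One-sided, formula | One-sided, simulated | Two-sided, formula | Two-sided, simulated |
|---|---|---|---|---|
| 164 | 80.2% | 80.6% | 70.1% | 70.5% |
| 149 | 76.7% | 77.2% | 65.9% | 66.4% |

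By formula, the drop-out step costs 80.2 − 76.7 = 3.5 points one-sided and 70.1 − 65.9 = 4.2 points two-sided. In the two-sided case the larger gap, from 80% to 70.1%, is already present at the full 164 pairs and has nothing to do with the drop-out allowance.

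**The case against.** The best defence concedes the arithmetic and argues that little depends on it. The calculation rests on a secondary outcome that the data analysis section says will be explored, in a study that describes itself as exploratory and exists to inform a later cluster-randomised trial. The primary outcomes are recruitment and drop-out, completeness of eIPOS and influence on care; 164 was not derived for any of them. No success threshold is tied to 213, and enrolling 213 rather than 235 would not bias an estimated recruitment or drop-out rate. The power loss attributable to the slip is about 3.5 points on the basis that reproduces 164. Quoting the two-sided 66% without its 70% comparator would overstate the effect.

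All of this stands, and it limits how much weight the point carries. It does not make 213 consistent with 164 pairs and 30% drop-out. One further possibility is that actual drop-out will be lower: the Strengths and limitations section cites around 20% in telehealth studies of heart failure and chronic obstructive pulmonary disease. At 20%, 213 × 0.80 = 170 pairs would suffice. But that is not the rate chosen for sizing this substudy; the protocol chose 30%.

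**Conclusion.** The concern holds. The enrolment of 213 is 164 with 30% added, and at 30% drop-out it leaves about 149 pairs instead of 164. The correct inflation of 164 is 235, so the target is 22 too low for its own assumptions. This part needs only the protocol's figures and simple arithmetic.

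The power figures rest on more: normally distributed differences, d = 0.20 and a choice of sidedness. Power at 149 pairs is about 77% one-sided and about 66% two-sided, so the stated 80% is missed either way. The part caused by the drop-out step is about 3.5 to 4 points. The figure 235 restores 80% power only if the 164, and hence a one-sided alpha of 0.05, is accepted. A two-sided test would need 208 pairs, or 208 / 0.70 = 297.1, i.e. 298 enrolled.

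The effect is modest and falls on a secondary comparison; the descriptive feasibility outcomes remain estimable. It is nonetheless a definite error in a stated planning figure, and should be corrected.

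**What to change.** Correct the sentence in one of three ways:
1. Give 235 as the enrolment that yields 164 pairs at 30% drop-out.
2. Keep 213 and state that at 30% drop-out it yields about 149 pairs, with about 77% power for d = 0.20 at one-sided alpha 0.05.
3. Keep 213 and state that it provides 164 pairs if drop-out does not exceed 23%.

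Whichever is chosen, state the sidedness of alpha in the same sentence, because every power figure depends on it. If the test is meant to be two-sided, 164 itself must be recalculated first.

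The cost is one sentence of wording. Options 2 and 3 need no extra patients; option 1 needs 22 more.
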